3 STUDY OBJECTIVES

3.1 Primary Objective

The primary objective is to determine the efficacy of targeted naltrexone versus placebo in reducing binge drinking among non-dependent MSM, as determined by number of binge drinking days in timeline follow-back (TLFB) over the three-month treatment period.

3.2 Secondary Objectives

To secondary objectives include 1) to determine the efficacy of targeted naltrexone versus placebo in reducing alcohol consumption among non-dependent MSM, as determined by the proportion of ethyl glucuronide (EtG) positive urines, over the three-month treatment period; 2) to determine the efficacy of targeted naltrexone versus placebo in reducing alcohol-associated sexual risk behaviors, we will use GEE Poisson models with robust standard errors for the four monthly ACASI assessments on numbers of male anal sex partners, HIV-serodiscordant unprotected anal sex partners, unprotected anal sex partners while intoxicated with alcohol, and unprotected anal sex events with serodiscordant partners, including the baseline value. In the event that these outcomes are severely over-dispersed, we will analyze indicators for any self-report of each behavior, using GEE logistic models.

4 STUDY DESIGN

4.1 Study Overview

This is a double-blind, placebo-controlled, two-arm trial in which 120 binge-drinking MSM will be randomly assigned to receive 12 weeks of oral naltrexone 50 mg or placebo, to be taken on an as needed basis. This efficacy study will enroll binge-drinking MSM because they are the most likely population to benefit from this intervention. A study clinician from the Center for Public Health Research (CPHR) will perform the Structured Clinical Interview for the DSM-IV (SCID) to determine eligibility and rule out alcohol dependence (the SCID for DSM-V will be used when it becomes available). Upon enrollment, 120 participants will be randomized 1:1 to naltrexone or placebo for targeted administration. Participants will be seen weekly for behavioral surveys, urinalyses, study drug dispensing and alcohol use counseling. Safety laboratory assessment, vital signs, and the audio computer assisted survey instrument (ACASI) will be completed monthly. Efficacy, tolerability, and acceptability (Specific Aims 1-4) will be assessed upon trial completion as measured by number of binge drinking occasions and numbers of drinks on drinking days via timeline follow-back at weekly visits; number of ethyl glucuronide-positive urine samples; sexual risk behavior data through monthly surveys via ACASI; frequency of adverse clinical events by treatment arm, and cumulative medication adherence data at week 12. Primary analyses are designed as “intention-to-treat” with evaluation of outcomes according to random assignment, regardless of whether participants took the medication.

5 CRITERIA FOR EVALUATION:

5.1 Primary Efficacy Endpoint

The primary efficacy endpoint is to detect 27% reductions in numbers of binge drinking occasions, as well as 10% reductions in the average numbers of drinks on drinking days among treatment arm compared to placebo arm. Using the assumptions for loss to follow-up for the primary endpoint, as well as estimates based on biomarker data from Batki et al's study on Topiramate for alcohol use disorders¹²² for the within-subject correlation and control group urine positivity rate, we estimate that the study will have 80% power in 2-sided tests with a type-I error rate of 5% to detect 15-23% reductions in the urine positivity rate in the treatment arm. The time course for the endpoints will be assessed from baseline to end of treatment period.

5.2 Secondary Efficacy Endpoints:

The secondary efficacy endpoint is based on estimates of within-subject correlation and control prevalence from our Project Echo trial, we estimate that the study will have 80% power to detect 31% reductions in numbers of male anal sex partners, 57% reductions in SDUA partners, 46%

reductions in UA partners while intoxicated with alcohol, and 56% reductions in UA events with serodiscordant partners. In analyses using GEE logistic models, we will have 80% power to detect reductions of 14%, 38%, 39%, and 30% in any report of these four sexual risk behaviors, respectively.

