ACASI	Audio Computer Assisted Survey Instrument
AE	adverse event
ALT	alanine aminotransferase
AST	aspartate aminotransferase
BUN	blood urea nitrogen
CBC	Complete blood count
CBO	Community based organization
CCG	Community Consulting Group
CFR	Code of Federal Regulations
CRF	case report form
CPHR	Center for public health research
DMC	Data Monitoring Committee
DSMB	Data Safety Monitoring Board
DSM-IV	Diagnostic and Statistical Manual for Mental disorders
EtG	ethylglucuronide test
FDA	Food and Drug Administration
GCP	Good Clinical Practice
GEE	generalized estimating equations
HIPAA	Health Insurance Portability and Accountability Act of 1996
HIV	Human Immunodeficiency Virus
ICF	informed consent form
ICH	International Conference on Harmonisation
IEC	Independent Ethics Committee
IRB	Institutional Review Board
MM	Medical Management counseling
MSM	Men who have sex with men
NIAAA	National Institute on Alcohol Abuse and Alcoholism
PEth	phosphatidylethanol
PrEP	pre-exposure prophylaxis
PI	Principal Investigator
SAE	serious adverse experience
SAMHSA	Substance Abuse and Mental Health Services Administration
SCID	Structural clinical interview for DSM disorders
SFDPH	San Francisco Department of Public Health
SMS	Text message
TLFB	Timeline follow-back

PROTOCOL SYNOPSIS

TITLE	The Better THAN Study: Targeting Heavy Alcohol use with Naltrexone among MSM
SPONSOR	[name]
FUNDING ORGANIZATION	National Institute on Alcohol Abuse and Alcoholism (NIAAA)
NUMBER OF SITES	1 site
RATIONALE	Oral naltrexone, FDA approved agent, was chosen because we believe it will be more acceptable to non-treatment seeking, non-alcohol dependent binge drinking men who have sex with men (MSM). Intermittent dosing makes sense for most binge-drinking MSM because data indicate that they do not binge drink daily.
STUDY DESIGN	This is a randomized, double-blind, placebo-controlled phase 2 study.
PRIMARY OBJECTIVE	To determine the efficacy of targeted naltrexone versus placebo in reducing binge drinking among non-dependent MSM, as determined by number of binge drinking days in timeline follow-back (TLFB), over the three-month treatment period.
SECONDARY OBJECTIVES	To determine the efficacy of targeted naltrexone versus placebo in reducing alcohol consumption among non-dependent MSM, as determined by the proportion of ethyl glucuronide (EtG) positive urines, over the three-month treatment period.
NUMBER OF SUBJECTS	120

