DURATION OF SUBJECT PARTICIPATION AND DURATION OF STUDY	Subjects will be on study for up to 9 months Screening: up to 30 days Treatment: 3 months Follow-up: 6 months The total duration of the study is expected to be nine months. One month for subject recruitment and nine months for final subject participation and follow-up.
CONCOMITANT MEDICATIONS	Allowed: standard therapy Prohibited: current use of/ dependence on any opioid medication or current naltrexone treatments.
EFFICACY EVALUATIONS	
PRIMARY ENDPOINT	
 • To detect 27% reductions in numbers of binge drinking occasions, as well as 10% reductions in the average numbers of drinks on drinking days among treatment arm compared to placebo arm.
SECONDARY ENDPOINTS	
 • To detect 15-23% reductions in the urine positivity rate in the treatment arm compared to the placebo arm.
OTHER EVALUATIONS	Potential biomarkers for alcohol: EtG and PEth
SAFETY EVALUATIONS	Change in clinical safety labs from baseline to week 12 Incidence of adverse events
PLANNED INTERIM ANALYSES	No planned interim analyses. Serious adverse events will be monitored by the committee on an ongoing basis throughout the study.

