STATISTICS Primary Analysis Plan	
We will use generalized estimating equations (GEE) to estimate treatment effects on repeated study outcomes. Primary analyses will be by intention-to-treat, without regard to adherence to treatment. In our prior trials, we had excellent retention and visit adherence. Nonetheless, in this high-risk population, missing data may be encountered.^{123, 124} We will conduct sensitivity analyses imputing all missing urine samples as positive, adjusting for baseline correlates of missingness, and using inverse probability of censoring weights.¹²⁵
 
Specific Aim 1: To determine the efficacy of targeted naltrexone versus placebo in reducing binge drinking among non-dependent MSM, as determined by number of binge drinking days in timeline follow-back (TLFB), by arm. GEE Poisson models with robust standard errors will be used to assess reductions on weekly drinking outcomes. Baseline TLFB results will be included in the analysis. Minimum detectable effects (MDEs): In calculating minimum detectable effects, we hypothesized on pharmacologic grounds that oral naltrexone will reach full efficacy against alcohol use almost immediately; accordingly we expect treatment-control differences to be approximately constant over the 12 weeks of the trial. Based on the prior trial (93% retention), we estimate that 90% of participants will be retained at 12 weeks. Using estimates based on data from Project ECHO⁹² for the within-subject correlation and over-dispersion of the outcomes, as well as the mean frequency among controls, we estimate that the proposed study will have 80% power in 2-sided tests with a type-I error rate of 5% to detect 27% reductions in numbers of binge drinking occasions, as well as 10% reductions in the average numbers of drinks on drinking days.
 
Specific Aim 2: To determine the efficacy of targeted naltrexone versus placebo in reducing alcohol consumption among non-dependent MSM, as determined by the proportion of ethyl glucuronide (EtG) positive urines, by arm. GEE logistic models with robust standard errors will be used to assess reductions frequency of positive urine tests, accounting for within-subject correlation. MDEs: Using the assumptions for loss to follow-up for Aim 1, as well as estimates based on biomarker data from Batki et al's study on Topiramate for alcohol use disorders¹²² for the within-subject correlation and control group urine positivity rate, we estimate that the study will have 80% power in 2-sided tests with a type-I error rate of 5% to detect 15-23% reductions in the urine positivity rate in the treatment arm.
 
Specific Aim 3: To determine the efficacy of targeted naltrexone versus placebo in reducing alcohol-associated sexual risk behaviors, we will use GEE Poisson models with robust standard errors for the four monthly ACASI assessments on numbers of male anal sex partners, HIV-serodiscordant unprotected anal sex partners, unprotected anal sex partners while intoxicated with alcohol, and unprotected anal sex events with serodiscordant partners, including the baseline value. In the event that these outcomes are severely over-dispersed, we will analyze indicators for any self-report of each behavior, using GEE logistic models. MDEs: Based on estimates of within-subject correlation and control prevalence from our Project Echo trial, we estimate that the study will have 80% power to detect 31% reductions in numbers of male anal sex partners, 57% reductions in SDUA partners, 46% reductions in UA partners while intoxicated with alcohol, and 56% reductions in UA events with serodiscordant partners. In

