15.3 Analysis of Primary Endpoint

To determine the efficacy of targeted naltrexone versus placebo in reducing binge drinking among non-dependent MSM, as determined by number of binge drinking days in timeline follow-back (TLFB), by arm. GEE Poisson models with robust standard errors will be used to assess reductions on weekly drinking outcomes. Baseline TLFB results will be included in the analysis. **Minimum detectable effects (MDEs):**

In calculating minimum detectable effects, we hypothesized on pharmacologic grounds that oral naltrexone will reach full efficacy against alcohol use almost immediately; accordingly we expect treatment-control differences to be approximately constant over the 12 weeks of the trial. Based on the prior trial (93% retention), we estimate that 90% of participants will be retained at 12 weeks. Using estimates based on data from Project ECHO⁹² for the within-subject correlation and over-dispersion of the outcomes, as well as the mean frequency among controls, we estimate that the proposed study will have 80% power in 2-sided tests with a type-I error rate of 5% to detect 27% reductions in numbers of binge drinking occasions, as well as 10% reductions in the average numbers of drinks on drinking days.

To determine the efficacy of targeted naltrexone versus placebo in reducing alcohol consumption among non-dependent MSM, as determined by the proportion of ethyl glucuronide (EtG) positive urines, by arm. GEE logistic models with robust standard errors will be used to assess reductions frequency of positive urine tests, accounting for within-subject correlation. **MDEs:** Using the assumptions for loss to follow-up for Aim 1, as well as estimates based on biomarker data from Batki et al's study on Topiramate for alcohol use disorders¹²² for the within-subject correlation and control group urine positivity rate, we estimate that the study will have 80% power in 2-sided tests with a type-I error rate of 5% to detect 15-23% reductions in the urine positivity rate in the treatment arm.

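### The primary endpoint is one outcome in four places and two in the sections that define it, with no rule for deciding success and no alpha allocation

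*Combined protocol and SAP*

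**What the plan says.** **One outcome.** Four places define primary efficacy by binge drinking days alone:

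- Synopsis, primary objective: "as determined by number of binge drinking days in timeline follow-back (TLFB), over the three-month treatment period".
- Section 3.1: "as determined by number of binge drinking days in timeline follow-back (TLFB) over the three-month treatment period".
- Synopsis, Specific Aim 1, and the opening of section 15.3: "as determined by number of binge drinking days in timeline follow-back (TLFB), by arm".

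**Two outcomes.** The two places whose job is to define the endpoint name a pair:

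- Synopsis, primary endpoint row: "To detect 27% reductions in numbers of binge drinking occasions, as well as 10% reductions in the average numbers of drinks on drinking days".
- Section 5.1: "The primary efficacy endpoint is to detect 27% reductions in numbers of binge drinking occasions, as well as 10% reductions in the average numbers" (meaning drinks per drinking day).

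The power text in Specific Aim 1 and section 15.3 claims 80% power in two-sided tests at 5% to "detect 27% reductions in numbers of binge drinking occasions, as well as 10% reductions in the average numbers of drinks on drinking days". Section 4.1 also lists both measures, without ranking them. No section gives a success rule, a test order or an alpha split.

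**Two related wording faults.** Text on ethyl glucuronide (EtG) sits under the primary headings in 5.1 and 15.3, although the synopsis and 3.2 make EtG secondary. Aim 1 and 15.3 define the outcome in days but state the 27% for occasions.

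**The concern.** The definition of the primary endpoint decides whether the trial is positive, and here it depends on which section is read. The stated 5% error rate and 80% power belong to a single test. They describe the whole trial only if one outcome is primary. Section 5.1 names two outcomes but not how they combine, so three decision rules remain open:

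| Result at two-sided 5% | 3.1: binge days only | 5.1: either is enough | 5.1: both needed |
|---|---|---|---|
| Binge outcome significant, drinks on drinking days not | positive | positive | negative |
| Drinks on drinking days significant, binge outcome not | negative | positive | negative |

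In each row a reader can reach opposite conclusions while citing the document correctly. A rule chosen after the results are known would not be credible.

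**Working it through.** **Inputs from the document.** Two-sided 5% and 80% power; detectable reductions of 27% and 10% (Aim 1, 15.3); 120 participants (15.6), randomised 1:1 (4.1); 90% retention at 12 weeks (15.3), so 0.9 × 60 = 54 per arm.

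**Input not in the document.** The correlation ρ between the two test statistics. I use 0 to 0.9. Both measures come from the same drinking reports, so ρ = 0 is best read as a bounding case.

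**The plan's own power figure.** It cannot be reproduced, because the control mean, over-dispersion and within-subject correlation are attributed to a source trial without values. Back-solving SE = |ln(1 − reduction)| / (1.960 + 0.842) gives:

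- 27%: 0.3147 / 2.802 = 0.112
- 10%: 0.1054 / 2.802 = 0.0376

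This is circular and confirms nothing. As a range, take weekly control mean μ of 1 to 2, dispersion φ of 1 to 2, exchangeable within-subject correlation r of 0.3 to 0.7 (all assumed), 12 weeks and 54 per arm:

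Var(log rate ratio) = φ(1 + 11r)/12 × (1/μ + 1/(0.73μ)) / 54

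Power for a 27% reduction then runs from 24% (μ = 1, φ = 2, r = 0.7) to 94% (μ = 2, φ = 1, r = 0.3). The 80% is neither confirmed nor refuted. The steps below take it as given for each test.

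**Step 1: binge days only.** One test at 5%. The decision rule costs no error and no power.

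**Step 2: either outcome is enough, each at 5%, both nulls true.** Error = 1 − P(|Z₁| ≤ 1.960 and |Z₂| ≤ 1.960), with Z₁ and Z₂ bivariate normal. At ρ = 0 this is 1 − 0.95² = 0.0975.

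**Step 3: both needed, each test with 80% power.** Each statistic has mean 2.802, so joint power = Φ₂(0.842, 0.842; ρ). At ρ = 0 this is 0.80² = 0.64.

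| ρ | 0 | 0.3 | 0.5 | 0.7 | 0.9 |
|---|---|---|---|---|---|
| Type-I error, either | 9.75% | 9.5% | 9.1% | 8.3% | 7.0% |
| Power, both | 64.0% | 66.6% | 68.7% | 71.3% | 75.0% |

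The error row depends on neither the effect sizes nor the unreported inputs. The power row moves with the assumed per-test power. At ρ = 0 / 0.5 / 0.9, joint power is 49% / 56% / 64% if each test has 70%, and 81% / 83% / 87% if each has 90%.

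**Step 4: cost of keeping both as primary.**

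- Both needed, 80% joint power: the sample-size factor is 1.313 / 1.247 / 1.121 at ρ = 0 / 0.5 / 0.9. At ρ = 0 each test needs √0.80 = 89.4% power, so the factor is ((1.960 + 1.250)/2.802)² = 1.313. Times 120, this is about 158 / 150 / 135 participants.
- Alpha split to 2.5% each (critical value 2.241): power per outcome = Φ(2.802 − 2.241) = 71%. The effects detectable with 80% power grow from 27% to 29.3% and from 10% to 10.9%.

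**The case against.** The best defence is that the intent is clear and only the drafting is poor. The endpoint sentence in 5.1 repeats the detectable-effect wording of Aim 1, and 5.2 has the same fault, so power text was probably pasted into the endpoint slots. Four places agree on one outcome. No section states an either-rule or a both-rule, so the inflated error and the lost power are hypothetical. Section 15 promises a detailed SAP, 8.2 keeps the blind until database lock, 15.5 excludes an interim analysis, and this is phase 2.

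Much of this is fair. One primary outcome is probably what was meant, which is why the fix adopts it. The error and power figures apply only if 5.1 is followed, and 80% power in a separate test of each outcome is the natural reading, not an explicit statement.

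It does not remove the problem. EtG can be set aside as misplaced because it is expressly secondary elsewhere, and its power text borrows from the primary: "Using the assumptions for loss to follow-up for the primary endpoint" in 5.1, "Using the assumptions for loss to follow-up for Aim 1" in 15.3. Drinks on drinking days has no such ranking anywhere, and the two places that define the endpoint call it primary. The modelling sentence in 15.3 speaks of drinking outcomes in the plural, so it does not settle the matter. The SAP is tied to the final analysis and not to unblinding, and nothing says it will resolve this point. Phase 2 status does not help, because the plan itself claims 5% and 80%.

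**Conclusion.** The concern holds and must be fixed. The contradiction is in the current text and affects the rule that decides whether the trial succeeded.

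- **Under 3.1** there is no multiplicity loss. The 80% itself stays unverified, and whether the 27% was computed for days or occasions is not stated. That mismatch is probably loose wording.
- **Under 5.1, either enough,** type-I error is 7.0% to 9.75% against the stated 5%.
- **Under 5.1, both needed,** power is 64% to 75% against the stated 80%, if both true effects equal the stated detectable effects.

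The ranges rest on an assumed correlation of 0 to 0.9 and on treating the two test statistics as bivariate normal.

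**What to change.** Before unblinding:

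1. In the synopsis endpoint row, 5.1 and 15.3, name one primary endpoint that matches 3.1: number of binge drinking days by timeline follow-back over the 12-week treatment period. The estimate is the between-arm rate ratio from the planned GEE Poisson model with robust standard errors, tested two-sided at 5%.
2. List average drinks on drinking days as secondary.
3. Remove the 27% and 10% from the endpoint statements. They already stand as detectable effects in Aim 1 and 15.3.
4. Move the EtG text from 5.1 to 5.2 and from 15.3 to 15.4.
5. Use days throughout the synopsis, 4.1, 5.1 and 15.3. Confirm that the 27% was computed for days, or restate it.

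This costs wording, and a restated detectable effect if the 27% was for another unit. It needs no new data and no change to the 120. The loss is that drinks on drinking days can no longer support a primary claim.

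Other explicit rules would also remove the ambiguity. Two required outcomes need about 135 to 158 participants. A 2.5% split leaves 71% power per outcome at 120. A fixed sequence with binge days first keeps its 5% and 80%, and the second claim then has the both-needed power of 64% to 75%. Any of these must be written down before unblinding.

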5.3 Safety Evaluations

Change in clinical laboratory findings, specifically the liver enzymes such as BUN or Creatinine.
Incidence of adverse events

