A review of the literature concluded that in patients treated for heroin or alcohol dependence, naltrexone does not cause clinically significant liver disease or exacerbate pre-existing liver disease.⁷¹ However, naltrexone has the capacity to cause hepatocellular injury in excessive doses and is contraindicated in acute hepatitis and liver failure.⁶⁹ Patients with these conditions will be excluded from our trial. Naltrexone is also contraindicated in patients who are currently dependent on opioids or in acute opioid withdrawal. The team anticipates that few participants will be excluded by virtue of current opioid use; for example, in our recently published mirtazapine study, only 7% of MSM met criteria for opioid dependence. Although the opioid blockade produced by naltrexone is surmountable, this situation requires careful medical management by trained personnel in settings equipped for resuscitation. Attempts by patients to overcome naltrexone's opioid antagonism may lead to an overdose. Naltrexone may also precipitate severe opiate withdrawal, including mental status change, nausea, vomiting, diarrhea, and dehydration in patients who are not opioid-free for a minimum of 7 to 10 days.⁶⁹ For this reason, urine opioid testing is needed to screen all potential participants for opioid use. Patients who have a foreseeable need for opioid pain management (e.g. potential elective surgery in the study period) will also be excluded. Additionally, all patients will be fully informed verbally and in the written consent form about the potential for overdose by attempting to overcome naltrexone's opioid antagonism.

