6.3 Exclusion Criteria

- (1) Any psychiatric (e.g. depression with suicidal ideation) or medical condition that would preclude safe participation in the study;
- (2) known allergy/previous adverse reaction to naltrexone;
- (3) current use of/ dependence on any opioids or a known medical condition which currently requires/may likely require opioid analgesics;
- (4) opioid-positive urine at enrollment;
- (5) current CD4 count < 200 cells/mm³;

- (6) moderate/severe liver disease (AST, ALT \geq 3 times upper limit of normal);
- (7) impaired renal function (creatinine clearance $<$ 50 ml/min);
- (8) currently participating in another intervention research study with potential overlap;
- (9) alcohol dependence as determined by SCID criteria (participants with non-dependent alcohol use disorders/symptoms of alcohol abuse [per DSM-IV] are *eligible*)
- (10) any condition that, in the principal investigator and/or study clinician's judgment interferes with safe study participation or adherence to study procedures;
- (11) not having a cell-phone that can send and receive text messages;

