9.3.2 Blood Chemistry Profile

Blood will be obtained and sent to San Francisco General Hospital Laboratory for determination of (list as applicable) serum sodium, potassium, chloride, bicarbonate, random glucose, BUN, creatinine, aspartate aminotransferase (AST/SGOT), alanine aminotransferase (ALT/SGPT), alkaline phosphatase, total bilirubin, direct bilirubin, gamma-glutamyl transferase (GGT), albumin and LDH.

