11 ADVERSE EXPERIENCE REPORTING AND DOCUMENTATION

11.1 Adverse Events

An adverse event (AE) is any untoward medical occurrence in a clinical investigation of a patient administered a pharmaceutical product and that does not necessarily have a causal relationship with the treatment. An AE is therefore any unfavorable and unintended sign (including an abnormal laboratory finding), symptom or disease temporally associated with the administration of an investigational product, whether or not related to that investigational product. An unexpected AE is one of a type not identified in nature, severity, or frequency in the current Investigator's Brochure or of greater severity or frequency than expected based on the information in the Investigator's Brochure.

The Investigator will probe, via discussion with the subject, for the occurrence of AEs during each subject visit and record the information in the site's source documents. Adverse events will be recorded in the patient CRF. Adverse events will be described by duration (start and stop dates and times), severity, outcome, treatment and relation to study drug, or if unrelated, the cause.

AE Severity

The National Cancer Institute's Common Terminology Criteria for Adverse Events (CTCAE) Version 3.0 should be used to assess and grade AE severity, including laboratory abnormalities judged to be clinically significant. The modified criteria can be found in the study manual. If the experience is not covered in the modified criteria, the guidelines shown in Table 1 below should be used to grade severity. It should be pointed out that the term "severe" is a measure of intensity and that a severe AE is not necessarily serious.

Table 1. AE Severity Grading

Severity (Toxicity Grade)	Description
Mild (1)	Transient or mild discomfort; no limitation in activity; no medical intervention or therapy required. The subject may be aware of the sign or symptom but tolerates it reasonably well.
Moderate (2)	Mild to moderate limitation in activity, no or minimal medical intervention/therapy required.
Severe (3)	Marked limitation in activity, medical intervention/therapy required, hospitalizations possible.
Life-threatening (4)	The subject is at risk of death due to the adverse experience as it occurred. This does not refer to an experience that hypothetically might have caused death if it were more severe.

AE Relationship to Study Drug

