15.4 Analysis of Secondary Endpoints

The analysis of the secondary endpoint to determine the efficacy of targeted naltrexone versus placebo in reducing alcohol-associated sexual risk behaviors, we will use GEE Poisson models with robust standard errors for the four monthly ACASI assessments on numbers of male anal sex partners, HIV-serodiscordant unprotected anal sex partners, unprotected anal sex partners while intoxicated with alcohol, and unprotected anal sex events with serodiscordant partners, including the baseline value. In the event that these outcomes are severely over-dispersed, we will analyze indicators for any self-report of each behavior, using GEE logistic models. **MDEs:** Based on estimates of within-subject correlation and control prevalence from our Project Echo trial, we estimate that the study will have 80% power to detect 31% reductions in numbers of male anal sex partners, 57% reductions in SDUA partners, 46% reductions in UA partners while intoxicated with alcohol, and 56% reductions in UA events with serodiscordant partners. In analyses using GEE logistic models, we will have 80% power to detect reductions of 14%, 38%, 39%, and 30% in any report of these four sexual risk behaviors, respectively.

Safety and tolerability data will be summarized by treatment group.

Adverse event rates will be coded by body system and MedDra classification term. Adverse events will be tabulated by treatment group and will include the number of patients for whom the event occurred, the rate of occurrence, and the severity and relationship to study drug.

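### Section 5.3 names BUN and creatinine as liver enzymes in the laboratory safety endpoint, and no later section corrects it; separately, Section 15.1 read literally makes eligibility a condition of the safety set

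*Combined protocol and SAP*

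**What the plan says.** **Laboratory endpoint.** Section 5.3 lists two safety evaluations: change in laboratory findings, and incidence of adverse events. It narrows the first to "specifically the liver enzymes such as BUN or Creatinine". The synopsis states the same endpoint without naming a test: "Change in clinical safety labs from baseline to week 12".

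**Liver and kidney elsewhere in the protocol.** Section 6.3 excludes "moderate/severe liver disease (AST, ALT" at or above three times the upper limit of normal) in criterion 6. Criterion 7 excludes "impaired renal function (creatinine clearance" below 50 ml/min). The chemistry panel in Section 9.3.2 includes "aspartate aminotransferase (AST/SGOT), alanine aminotransferase (ALT/SGPT"), bilirubin and GGT, and also BUN and creatinine. Section 9.1.6 schedules safety laboratory tests at screening and at months 1, 2 and 3.

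**Hepatic risk.** Section 2.1 reports a literature review that found no clinically significant liver disease caused by naltrexone, and no worsening of existing liver disease, in patients treated for heroin or alcohol dependence. It then says that "naltrexone has the capacity to cause hepatocellular injury in excessive doses".

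**Analysis.** Section 15.4 says "Safety and tolerability data will be summarized by treatment group" and goes on to describe only the adverse-event tables. The opening of Section 15 promises a detailed SAP before the final data are analysed.

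**Safety set.** Section 15.1 defines the Safety Population by three conditions: eligible, randomised, and at least one dose taken. Section 13 lists failure to meet the entry criteria among the protocol violations and leaves any withdrawal to the PI.

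**The concern.** Section 5.3 is the only endpoint or analysis text that names a laboratory test, and its examples do not belong to the class it names. A reader cannot tell whether the endpoint is hepatic, as the noun says, or renal, as the examples say. An analyst who took the examples at face value could table change in BUN and creatinine as the liver result. The tests the protocol itself uses to define liver disease would then have no named place in the safety report. The error could also pass into the SAP, because the SAP will be written from this text.

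The safety set raises a different question. A safety set normally follows exposure. If eligibility is an added condition, a dosed participant later found to have failed a criterion would drop out of the by-arm safety tables, although the drug exposure was real.

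**Working it through.** No arithmetic applies. Neither point rests on a power figure, an effect size or an event rate. The check sets the sections side by side.

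**Step 1: which organ does each named test belong to in this protocol?**

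| Test | Named in 5.3 as | Use in 6.3 | In the 9.3.2 panel |
|---|---|---|---|
| BUN | liver enzyme (example) | not used | yes |
| Creatinine | liver enzyme (example) | renal function, as creatinine clearance | yes |
| AST | not named | liver disease | yes |
| ALT | not named | liver disease | yes |

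Of the 2 tests named in 5.3, 0 are the protocol's liver markers and 1 (creatinine) is its renal measure. The protocol assigns BUN to no organ. Calling it a renal measure is ordinary laboratory usage and not a statement in the document. The contradiction therefore rests on Section 6.3. Section 9.3.2 is one undivided list, which shows that the tests are distinct and collected but does not sort them by organ.

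**Step 2: does another section correct 5.3?** Three places could do so.

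- The synopsis safety row covers all safety laboratory tests and adds a time frame (baseline to week 12) that 5.3 lacks, but it names no test.
- Section 15.4 says safety data are summarised by arm, but it names no laboratory test.
- The opening of Section 15 defers to a SAP yet to be written.

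None of them says which tests are the hepatic measures.

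**Step 3: are the data there?** Yes. AST and ALT are in the panel (9.3.2), which is drawn at screening and months 1 to 3 (9.1.6). Chemistry is drawn again at early withdrawal (10.6).

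**Step 4: the safety set.** Section 15.1 requires eligible, randomised and dosed. Section 13 foresees participants who are enrolled without meeting the criteria and, at the PI's discretion, not withdrawn. Taken literally, such a participant who has taken a dose meets two of the three conditions and falls outside the set. The documents give no count of such participants, so no size can be computed.

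**The case against.** The strongest reply is that this is a one-line drafting slip. Section 5.3 does name the right class, liver enzymes, and only the examples are wrong. The synopsis also specifies the endpoint, more broadly, and under its wording no collected liver test is left out. Section 15.4 already promises a summary by arm, and the SAP can supply the detail. Most of Section 15 deals with efficacy, demographics or sample size, so its silence on AST and ALT proves little. All of this stands, and it is why the point is minor. It does not remove the contradiction between 5.3 and 6.3. A SAP still to be written is a reason to correct the source text now.

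A reader might infer that liver injury would go unseen. The documents do not support that. Liver tests are collected, Section 11.1 provides for grading "laboratory abnormalities judged to be clinically significant", and under Section 14 the monitoring board receives relevant laboratory data by group. Nor should the hepatic sentence in Section 2.1 be read alone: it concerns excessive doses and follows a reassuring literature review.

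On the safety set, the reply is that the word eligible is probably descriptive. Section 8.1 uses it simply for the people who are randomised, and Section 15.1 states no rule for removing anyone. That is a fair reading, and this note is held with only moderate confidence. A reader might also infer that events in ineligible participants would be lost. They would not: Section 11.2.1 has all serious events documented. What is at stake is their place in the by-arm table.

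**Conclusion.** The main point holds with high confidence. Section 5.3 misidentifies the tests in the laboratory safety endpoint, it contradicts Section 6.3, and no other section puts it right. The error lies in the endpoint definition. It does not affect data collection, safety monitoring or the efficacy analysis. It would do harm only if an analyst or the SAP author followed the examples in 5.3 and not the synopsis.

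The safety-set note holds only on a literal reading of Section 15.1. The number affected is unknown and probably small, and no size is claimed.

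Severity: minor for both.

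**What to change.** - **Section 5.3:** name AST and ALT, already in the 9.3.2 panel, as the hepatic measures. List BUN and creatinine separately as renal measures. Align the time frame with the synopsis (baseline to week 12).
- **Section 15.4:** add that the hepatic and renal measures are summarised by treatment group, and carry the same wording into the SAP.
- **Section 15.1:** delete the word eligible, so that the Safety Population is all randomised participants who received at least one dose.

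The cost is three wording changes in the protocol, repeated in the SAP. No new data, visits or tests are needed, and no clinical rule changes.
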